1.3 Study Rationale

Given the role of B cells in the pathophysiology of chronic GvHD, the association between elevated BAFF levels post-transplant in abnormal B-cell homeostasis and chronic GvHD, and the efficacy of belimumab in the inhibition of BAFF signaling, these proof-of-principle findings support the rationale for use of belimumab as prophylaxis of chronic GvHD. We propose a pilot and feasibility study to assess the safety and tolerability, as well as preliminary efficacy, of belimumab as prophylaxis of chronic GvHD following alloHCT. Our central hypothesis is that belimumab will be well tolerated and have a favorable effect on incidence and severity of chronic GvHD.

2 STUDY OBJECTIVES

2.1 Primary Objective

To evaluate safety and tolerability of belimumab as prophylaxis of chronic GvHD in subjects following alloHCT. This will be assessed by CTCAE v. 4.03.

2.2 Secondary Objectives

1. To evaluate the impact of prophylactic belimumab on the incidence and severity of chronic GvHD at 6, 12 and 24 months after alloHCT
2. To evaluate the impact of prophylactic belimumab on the incidence and severity of acute GvHD at 3 and 6 months after alloHCT
3. To evaluate the impact of prophylactic belimumab on overall survival at 6, 12 and 24 months after alloHCT
4. To evaluate the impact of prophylactic belimumab on relapse rate at 6, 12 and 24 months after alloHCT
5. To evaluate the impact of prophylactic belimumab on overall corticosteroid requirement (dose and duration) for treatment of chronic GvHD at 6, 12 and 24 months after alloHCT
6. To evaluate the impact of prophylactic belimumab on the necessity to use alternative treatment modalities for chronic GvHD at 6, 12 and 24 months after alloHCT

2.3 Exploratory Objectives

1. To evaluate the effect of prophylactic belimumab on post-transplant immune cell reconstitution.
2. To explore candidate biomarkers (i.e. BAFF level, BAFF:B cell ratio; B cell subpopulation frequency) that could predict subjects who may benefit from prophylactic administration of belimumab to prevent chronic GvHD.

3 PATIENT SELECTION AND ENROLLMENT

3.1 Inclusion Criteria

1. At least 18 years of age
2. ECOG performance status ≤ 2
3. Diagnosis of hematologic malignancy (i.e. acute myeloid leukemia, acute lymphoblastic leukemia, chronic lymphocytic leukemia, chronic myelogenous leukemia, Hodgkin's lymphoma, non-Hodgkin's lymphoma, myelodysplastic syndrome, chronic myelomonocytic leukemia)
4. Use of myeloablative or non-myeloablative conditioning regimen
5. Use of mobilized peripheral blood stem cells from fully HLA-matched related or unrelated donor as a graft source
6. Acute GvHD prophylaxis with methotrexate and tacrolimus
7. Documented complete remission and full donor engraftment (by STR identity testing) on Day +30 bone marrow biopsy
 - a. Complete remission: less than 5% blasts in an aspirate bone marrow sample with a count of at least 200 nucleated cells, no blasts with Auer rods or persistence of extramedullary disease PLUS absolute neutrophil count (ANC) $> 1,500/\mu\text{L}$, platelet count $\geq 50,000/\mu\text{L}$ and no leukemic blasts in the peripheral blood.
 - b. Negative minimal residual disease
 - c. Full donor engraftment by STR testing (either by bone marrow or peripheral blood testing)
8. Adequate end organ function:
 - a. Serum bilirubin $\leq 1.5 \times \text{ULN}$
 - b. Alanine aminotransferase (ALT) and aspartate aminotransferase (AST) $\leq 2.5 \times \text{ULN}$
 - c. Creatinine clearance $\geq 40 \text{ mL/min/1.73 m}^2$ by the Cockcroft-Gault formula
9. Women of childbearing potential must agree to use adequate contraception (hormonal or barrier method of birth control, abstinence) prior to study entry, for the duration of study participation, and for 16 weeks after the last dose of study drug. Should a woman become pregnant or suspect she is pregnant while participating in this study, she must inform her treating physician immediately.
10. Able to understand and willing to sign an IRB-approved written informed consent.

3.2 Exclusion Criteria

1. Active grade III-IV classic acute GvHD; subjects with prior resolved acute GvHD on stable doses of immunosuppression at time of enrollment will be permitted
2. Evidence of classic chronic GvHD or overlap chronic GvHD at time of enrollment
3. Subjects who participated in a clinical trial of acute GvHD prophylaxis in which chronic GvHD was a secondary end point
4. Donor lymphocyte infusion administered to treat relapse or loss of donor chimerism
5. Treatment with rituximab or other anti-B cell specific antibodies within previous 3 months
6. History of other malignancy \leq 5 years previous with the exception of basal cell or squamous cell carcinoma of the skin which were treated with local resection only or carcinoma *in situ* of the cervix
7. Currently receiving any other investigational agents
8. Known allergy or intolerance to any component of belimumab, including human or murine proteins or monoclonal antibodies
9. Uncontrolled intercurrent illness including, but not limited to, ongoing or active infection, symptomatic congestive heart failure, unstable angina pectoris, cardiac arrhythmia, or psychiatric illness/social situations (including current drug or alcohol abuse or dependence, or history of drug or alcohol abuse or dependence within the last year) that would limit compliance with study requirements
10. Use of parenteral (IV or IM) antibiotics (antibacterials, antivirals, anti-fungals, or anti-parasitic agents) within 14 days prior to planned start of therapy
11. Evidence of serious suicide risk including any history of suicidal behavior in the last 6 months and/or any suicidal ideation in the last 2 months and/or poses a significant suicide risk in the judgment of the investigator
12. History of pre-existing immunodeficiency disorder, autoimmune condition, or chronic infection
13. Known HIV positivity
14. Serologic evidence of current or past hepatitis B infection based on the results of testing for HBsAg and anti-HBc – Patients positive for HBsAg or HBcAb are excluded
15. Positive test for hepatitis C antibody (patients with documented clearance of hepatitis C by PCR following treatment will be permitted)
16. Currently on therapy for active chronic infection (such as tuberculosis, pneumocystis, cytomegalovirus, herpes simplex virus, herpes zoster and atypical mycobacteria). Prophylactic therapy is allowed.
17. Has any other clinically significant abnormal laboratory value in the opinion of the investigator

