1.1 Graft-versus-Host Disease

Chronic graft-versus-host disease (GvHD) is the most common cause of late morbidity and non-relapse mortality following alloHCT, occurring in roughly 40-60% of long-term survivors [1-3]. Risk factors for developing chronic GvHD include older patient age, use of peripheral blood stem cells versus bone marrow, and lack of T-cell depletion [4, 5]. Chronic GvHD is a multisystem, debilitating, immune-mediated disorder characterized by immunosuppression and immune dysregulation, resulting in increased risk of infections, impaired organ function and reduced quality of life (QOL). Importantly, the incidence of GvHD is on the rise due to multiple factors, including more transplantation of older adults, increased use of mobilized peripheral blood as a stem cell source, increased use of alternative donors (i.e., unrelated or haploidentical donors), and improved early post-transplant survival. Symptoms of chronic GvHD occur gradually, starting on average at 6 months after transplantation. Chronic GvHD targets skin, mouth, eyes, gut, liver, lungs, joints, and genitourinary system; it may be restricted to a single site, but more frequently several organ-sites are included.

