5.6.2 Prohibited Medications

After prior B-cell therapy, there must be a wash-out of 5 therapeutic half-lives, when pharmacodynamic effect would be minimal (e.g., one year following rituximab).

From the time of initiation of conditioning regimen subjects must not have received any biologic investigational agent (i.e. any drug not approved for sale in the country in which it is being used).

For 30 days prior to administration of belimumab (or 5 half-lives, whichever is greater) subjects must not have received any non-biologic investigational agent (i.e. any drug not approved for sale in the country in which it is being used).

Live vaccines should not be given within 30 days prior to administration of belimumab or concurrently with belimumab.

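### Exclusion 3 covers earlier acute GvHD prophylaxis trials only where chronic GvHD was a secondary endpoint, leaving a narrow gap that other rules close only in part

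*Combined protocol and SAP*

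**What the plan says.** The Synopsis and Section 3.2 give exclusion 3 in the same words: "Subjects who participated in a clinical trial of acute GvHD prophylaxis in which chronic GvHD was a secondary end point". Four other rules bear on earlier treatment:

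- Inclusion 6 (Section 3.1): "Acute GvHD prophylaxis with methotrexate and tacrolimus".
- Exclusion 5 (Section 3.2): "Treatment with rituximab or other anti-B cell specific antibodies within previous 3 months".
- Exclusion 7 (Section 3.2): "Currently receiving any other investigational agents".
- Section 5.6.2, on biologics: "From the time of initiation of conditioning regimen subjects must not have received any biologic investigational agent". On other agents: "For 30 days prior to administration of belimumab (or 5 half-lives, whichever is greater) subjects must not have received any non-biologic investigational agent". In both sentences an investigational agent means "any drug not approved for sale in the country in which it is being used".

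Section 4.1 ties eligibility to the inclusion and exclusion criteria. The prior-agent rules of Section 5.6.2 are not listed in full among them.

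Chronic GvHD incidence and severity is the first secondary endpoint (Sections 2.2 and 8.2). Section 13 plans a 90% exact binomial interval for preliminary efficacy, a comparison with roughly 100 banked institutional subjects, and use of the data to size a phase II cohort. It plans no hypothesis test. The primary endpoint is safety and tolerability.

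**The concern.** Exclusion 3 sets two conditions: the earlier trial concerned acute GvHD prophylaxis, and chronic GvHD was a secondary endpoint in it. The plan gives no reason for the criterion. The natural reading is that it keeps out people whose chronic GvHD risk may already have been altered by another intervention. That reason applies at least as well to a trial that made chronic GvHD its primary endpoint, or that tested chronic GvHD prophylaxis outright, yet the wording reaches neither.

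The plan recognises that what happens around transplant affects this outcome. Section 1.1 lists "use of peripheral blood stem cells versus bone marrow, and lack of T-cell depletion" among the risk factors. In a single-arm study of 10, a lower risk brought in from an earlier trial cannot be told apart from a belimumab effect. The comparison may not absorb it either. Section 8.3 matches controls on age, disease, conditioning regimen and donor source or mismatch status, and Section 13 on age, disease and donor. Neither names GvHD prophylaxis or trial participation. At stake are the descriptive chronic GvHD estimate, the tissue-bank comparison and the phase II planning that draws on them.

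**Working it through.** **Plan's own figures.** The plan gives no number on this point. Its binomial statements for N = 10 concern serious adverse events, and they reproduce: 1 − 0.80^10 = 0.893 against the stated 90%; and 1 − 0.95^10 − 10 × 0.05 × 0.95^9 = 0.086 against the stated figure of under 10%. Nothing below depends on them.

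**Step 1. Who is caught.** Take a subject from an earlier prophylaxis trial that exclusion 3 does not reach.

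| Earlier trial treatment | Rule that applies | Result |
|---|---|---|
| Any investigational agent, still being given | Exclusion 7 | Excluded |
| Unapproved biologic, given from the start of conditioning onward | Section 5.6.2 | Barred, whatever the trial's endpoint |
| Anti-B-cell antibody within 3 months | Exclusion 5 | Excluded |
| Unapproved non-biologic, inside the washout | Section 5.6.2 | Barred |
| Unapproved non-biologic, past the washout | None | Not caught |
| Marketed drug or biologic (not a recent anti-B-cell antibody) added to methotrexate and tacrolimus, trial treatment finished | None | Not caught |

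The last row arises because Section 5.6.2 defines investigational by approval status, and because inclusion 6 requires a backbone without forbidding an addition.

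**Step 2. The washout window.** The washout is the larger of 30 days and 5 half-lives. It is 30 days when the half-life is at most 30 / 5 = 6 days. Sections 5 and 5.2 allow a first dose up to Day +80, so such an agent could be given until Day 80 − 30 = +50. Section 5.2 also states Day +60 for Cycle 1; on that limit the last day is 60 − 30 = +30.

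**Step 3. Size, by illustration.** Let k of 10 subjects come from such trials, p be the chronic GvHD risk without the earlier intervention, and r the risk ratio of that intervention. With no belimumab effect, expected incidence is

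p × [1 − (k/10)(1 − r)].

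The values of k and r are not in the documents; r = 0.5 is an assumption. For p, Section 1.1 gives 40–60% among long-term survivors, which stands in here for the risk in enrolled subjects.

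| p | k = 1 | k = 2 | k = 3 |
|---|---|---|---|
| 40% | 38% | 36% | 34% |
| 50% | 47.5% | 45% | 42.5% |
| 60% | 57% | 54% | 51% |

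At p = 50%, each affected subject removes 0.25 expected events (0.50 − 0.25), or 2.5 percentage points.

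**Step 4. Against the planned precision.** The exact 90% limits for x of n are the 5% quantile of Beta(x, n − x + 1) and the 95% quantile of Beta(x + 1, n − x).

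- 5/10: 22% to 78%
- 4/10: 15% to 70%
- 3/10: 9% to 61%

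A whole event moves the estimate by 10 points, but Step 3 implies only a quarter of an event per affected subject at p = 50%. Even k = 3 (7.5 points) is small beside an interval about 56 points wide. Section 8.2 requires at least 2 cycles for secondary endpoints, so the denominator may fall below 10; 4/8 gives 19% to 81%.

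**The case against.** The strongest reply is that the gap is narrow and its effect hypothetical.

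- **Other rules do much of the work.** A reader might infer that everyone from a trial with chronic GvHD as the primary endpoint stays eligible. The documents do not support that. Section 5.6.2 bars any unapproved biologic from the start of conditioning whatever the earlier endpoint, which includes an unapproved T-cell-depleting biologic given from then on. This stands, and it confines the point to the last two rows of the Step 1 table.
- **The missed class may be small or empty.** In a trial of acute GvHD prophylaxis, chronic GvHD would ordinarily be a secondary endpoint. Nothing in the documents shows that a trial of the omitted kind was recruiting. This stands as a limit on size, but it does not repair the wording.
- **Endpoint rank is not effect size.** A reader might infer that these subjects are the worst confounders. The documents rank no confounders, the earlier intervention may have had no effect, and the subject may have been in its control arm. This stands.
- **The rewording would not reach treatment outside a trial.** Marketed T-cell depletion given as routine care could matter as much, and an exclusion based on trial participation leaves it untouched. Matching on conditioning regimen may handle part of it. This also stands: the fix makes the criterion coherent but does not remove every such difference.
- **The consequence is limited.** The primary endpoint is safety, there is no test, and imprecision at N = 10 far exceeds the illustrated shift. This stands and lowers the priority.

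What survives all of this is that the criterion as written admits subjects whom its apparent purpose covers at least as strongly as those it excludes, and no other section fully closes the gap.

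**Conclusion.** The point holds as a narrow drafting gap of low consequence. Exclusion 3 omits trials with chronic GvHD as a primary or co-primary endpoint and trials of chronic GvHD prophylaxis. The other rules leave uncovered a completed trial of a marketed drug (other than a recent anti-B-cell antibody), or of a washed-out non-biologic investigational agent, added to methotrexate and tacrolimus.

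If such subjects enrol and the earlier intervention reduced chronic GvHD, the estimate would be lowered. The comparison could lean toward apparent benefit unless the controls were similarly affected. Under an assumed halving of risk, the shift is 2 to 3 percentage points per affected subject across baseline risks of 40–60%. A reader might conclude that the efficacy result will be biased toward benefit. That goes too far, because both the number of affected subjects and the effect of any earlier intervention are unknown.

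The conclusion rests on a literal reading, on taking inclusion 6 to permit an added agent, and on an inferred purpose for the criterion. The primary safety analysis is not touched.

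**What to change.** 1. In the Synopsis and Section 3.2, reword exclusion 3 to cover *participation in an interventional trial of acute or chronic GvHD prophylaxis with chronic GvHD as a primary or secondary endpoint*.
2. Apply the same rule when selecting tissue-bank controls (Sections 8.3 and 13), so that both sides of the comparison are restricted alike.
3. Reconcile Section 3.2 with Section 5.6.2, so that the eligibility list and the prior-agent restrictions agree. This includes the intervals after anti-B-cell therapy: exclusion 5 uses 3 months, while Section 5.6.2 gives one year after rituximab as its example. Which interval applies is for the investigators to settle.
4. If enrolment is complete, report prior prophylaxis-trial participation for each subject, and show chronic GvHD incidence with and without those subjects.

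The cost is a short text amendment, with no new procedures, and a slightly smaller eligible pool. Item 4 needs only a check of transplant records and one extra descriptive line.

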5 TREATMENT OF SUBJECTS AND STUDY DESIGN

This is a single center, open-label pilot and feasibility study of prophylactic belimumab for the prevention of chronic GvHD following alloHCT at Washington University School of Medicine in St. Louis. The study will include Screening Phase, Treatment Phase, and Follow-up Phase.

Subjects will be screened for the study after obtaining the results from their standard-of-care Day +30 bone marrow biopsy. Those subjects meeting the Inclusion and Exclusion Criteria will be enrolled in the study and start treatment between Day +30 and Day +80 after alloHCT. At enrollment, subjects may continue on steroids that were used to treat acute GvHD. At the time of enrollment, however, subjects should be responding to therapy and the dose of steroid should be ≤ 0.5 mg/kg/day of prednisone equivalent with no dose increase in the preceding 1 week. Subjects may also remain on other systemic immunosuppressive drugs that were used to prevent or treat acute GvHD. At the time of enrollment, acute GvHD should be grade II or less. Subjects diagnosed with or treated for chronic GvHD will be excluded from the study. The study population will include 10 subjects. Planned duration of treatment is for 7 cycles (6 months; see study schema). Subjects will be followed for 24 months. One of the secondary endpoints is to evaluate the impact of

belimumab on incidence and severity of chronic GvHD. The subjects who develop chronic GvHD while receiving treatment with the study drug, belimumab, may continue on the study at the discretion of treating transplant physician with careful documentation of their GvHD severity and treatments used for it. If at any point it is considered that the study drug may be contributing to chronic GvHD it will be discontinued.

The primary endpoint is safety and tolerability of belimumab. Subjects who receive at least one dose of belimumab will be eligible for primary endpoint analysis and it will be performed according to the CTCAE v4.03.

Diagnosis of chronic GvHD will be per NIH criteria (**Appendix B**). Those patients diagnosed with chronic GvHD will have organ specific staging and global scoring according to the NIH criteria (**Appendices D and E**).

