5.2 Study Drug Administration

Belimumab will be administered intravenously at 10 mg/kg over 1 hour. Enrollment and the first dose of belimumab (Cycle 1) will be administered between Day +30 and Day +80 after alloHCT, after reviewing bone marrow biopsy results and confirming eligibility. Subjects will receive belimumab every 2 weeks for 3 cycles and then every 4 weeks for a total of 7 cycles (6 months of therapy).

Therefore: Cycle 1 of belimumab will be administered between Day +30 and +60 after alloHCT, Cycle 2 will be administered 2 weeks later (+/- 3 days), Cycle 3 will be administered two weeks after Cycle 2 (+/- 3 days), and each subsequent cycle will be given every 4 weeks thereafter (+/- 1 week) for total of 7 cycles (6 months of therapy). This dosing and schedule of belimumab administration is similar to prior phase III studies for systemic lupus erythematosus [38, 39]. Subjects will continue to adjust their standard of care immunosuppressive medications at the discretion of treating physician.

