10 STUDY CALENDAR

10.1 Screening and Treatment Calendar

	Screening ¹	Baseline ²	C1	C2 +2wk	C3 +4wk	C4 +8wk	C5 +12wk	C6 +16wk	C7 +20wk
Informed consent	X								
H&P, ECOG PS	X		X	X	X	X	X	X	X
VS	X		X	X	X	X	X	X	X
CBC	X		X	X	X	X	X	X	X
CMP, LDH, phosphate, uric acid, magnesium	X		X	X	X	X	X	X	X
Pregnancy test ⁷	X		X ⁸	X	X	X	X	X	X
IgG and IgA		X							
Hepatitis serologies	X								
ECG (triplicate)	X		As clinically indicated						
Belimumab			X ⁵	X ⁵	X ⁵	X ⁶	X ⁶	X ⁶	X ⁶
Research blood		X ²			X ⁴				
Acute GvHD assessment		X			X	X	X	X	X
Chronic GvHD assessment					X	X	X	X	X
Immunosuppressive medication assessment	X	X	X	X	X	X	X	X	X
Medication reconciliation		Monthly							
AE assessment		X ----- X ⁹							

1. Screening assessments must take place between 30 and 80 days post-transplant
2. pre-treatment
3. Every 3 months starting at F/U #1 (+24wk)
4. Prior to treatment
5. Dosing window is +/- 3 days
6. Dosing window is +/- 1 week
7. Women of childbearing potential only
8. Pregnancy test need not be repeated on Cycle 1 if conducted within 7 days of Cycle 1 dose
9. AE assessment continues for 30 days post-EOT

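### Exclusion 5 and Section 5.6.2 set different anti-B-cell wash-outs, so a patient treated 3 to 12 months before entry can be enrolled in breach of 5.6.2; separately, Section 5.2 gives two first-dose windows (minor)

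*Combined protocol and SAP*

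**What the plan says.** **Wash-out.** Section 3.2, item 5, and the same item in the synopsis, exclude "Treatment with rituximab or other anti-B cell specific antibodies within previous 3 months". Section 5.6.2 states: "After prior B-cell therapy, there must be a wash-out of 5 therapeutic half-lives, when pharmacodynamic effect would be minimal (e.g., one year following rituximab". No text ranks or links the two rules, and neither names the date from which the interval is counted back. Section 4.1 requires proof, before the first dose, that every inclusion criterion is met and no exclusion criterion applies. It does not mention Section 5.6.2.

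**First dose.** Section 5.2 first says that "the first dose of belimumab (Cycle 1) will be administered between Day +30 and Day +80 after alloHCT". Its next paragraph says that "Cycle 1 of belimumab will be administered between Day +30 and +60 after alloHCT". Section 5 has subjects "enrolled in the study and start treatment between Day +30 and Day +80 after alloHCT", the synopsis and schema also use Day 80, and a footnote to the calendar in Section 10.1 reads "Screening assessments must take place between 30 and 80 days post-transplant".

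**The concern.** These are two separate inconsistencies, each between a rule and its own counterpart.

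The wash-out is the weightier one. Section 5.6.2 itself treats the B-cell effect of earlier therapy as minimal only after the longer interval, yet the criterion checked at entry uses the shorter one. The trial admits lymphoma, CLL and ALL, so earlier anti-B-cell antibody treatment is plausible. Section 9 reads B-cell reconstitution and BAFF levels as effects of belimumab, and BAFF:B-cell ratio is a candidate biomarker. A patient still under the effect of an earlier antibody would blur that reading.

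The planned data might not show who these patients are. Section 5.1.2 records active medication from 30 days before consent, plus treatments for GvHD. Rituximab given for lymphoma six months earlier falls under neither. Section 5.1.1 collects medical and disease history but does not ask for the date of the last antibody. Sections 8.3 and 13 do not list earlier anti-B-cell therapy among the factors for matching controls.

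The first-dose window raises a smaller question: whether a first dose on Days +61 to +80 is a protocol deviation.

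**Working it through.** **The plan's own figures (Section 13, n = 10).**
- Chance of at least one SAE at a true rate of 20%: 1 − 0.8^10 = 0.893 (stated 90%).
- Chance of two or more at 5%: 1 − 0.95^10 − 10 × 0.05 × 0.95^9 = 1 − 0.599 − 0.315 = 0.086 (stated below 10%).

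Both reproduce, and neither depends on the wash-out or the window.

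**Wash-out rules side by side (rituximab).**

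| Last dose before entry | Section 3.2, item 5 | Section 5.6.2 example |
|---|---|---|
| Within 3 months | Excluded | Not washed out |
| More than 3 months, less than 1 year | Admitted | Not washed out |
| 1 year or more | Admitted | Washed out |

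The disputed zone is 12 − 3 = 9 months wide. If one year equals five half-lives, the implied half-life is 365 / 5 = 73 days, and 3 months (taken as 90 days) is 90 / 73 = 1.2 half-lives on the protocol's own measure.

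**Where that exposure falls.** Assumption: both intervals count back from the first dose, on Day D, with D from +30 to +80.
- Latest exposure that passes item 5: D − 90, which is Day −60 for D = 30 and Day −10 for D = 80. All of it precedes transplant.
- End of the one-year interval for that latest exposure: (D − 90) + 365 = D + 275, which is Day +305 to Day +355, or about 9 months after the first dose.

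**Which readouts that touches.**
- Inside: the baseline and pre-Cycle 3 samples, the 6-month visit, and chronic GvHD at 6 months after transplant.
- At the edge: the 9-month visit (about 274 days after the first dose).
- Outside: chronic GvHD assessed at 12 and 24 months after transplant (from Day 365), and the additional B-cell phenotyping that Section 9 expects at 18 to 24 months.

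**How many patients.** The documents do not say. For an assumed share q of entrants in the zone, the chance of at least one among 10 is 1 − (1 − q)^10:

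| Assumed q | Chance of at least one |
|---|---|
| 5% | 40% |
| 10% | 65% |
| 20% | 89% |
| 30% | 97% |

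Each patient is 1/10, or 10 percentage points, of a proportion based on all ten.

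**First-dose window.** Day +30 to +80 spans 80 − 30 + 1 = 51 days and Day +30 to +60 spans 31. Days +61 to +80 are 20 days, or 20 / 51 = 39% of the longer window's calendar days (not of patients). Someone screened in those 20 days, as Section 10.1 permits, cannot meet the Day +60 limit.

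**The case against.** Both wash-out rules are restrictions and can be met together. Section 5.6.2 is mandatory, so if it is followed the longer interval governs and nobody in the zone is dosed. That is a fair reading, but the entry procedure does not enforce it, because Section 4.1 checks only the two lists of criteria. This part of the concern stands.

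Other parts of the defence succeed and limit the point:
- A reader might infer that rituximab given to prevent chronic GvHD is let through. Section 1.1.2 does describe such use, with infusion 2 to 3 months after transplant. But with a first dose by Day +80, any rituximab given between transplant and entry lies within the previous 3 months and is already barred by item 5.
- Entrants have had conditioning and show full donor engraftment, which weakens the carry-over argument. A baseline research sample is also taken.
- Controls are matched on disease and conditioning (Section 8.3), and their medication lists are described as available.
- A reader might infer a shift in chronic GvHD from, say, 5/10 to 4/10. That supposes that such a patient is enrolled and that the earlier antibody alone prevented the disease. The documents support neither. The 90% exact intervals, 22.2% to 77.8% and 15.0% to 69.6%, overlap almost entirely, and no hypothesis is tested.
- Day +60 appears once, against Day 80 everywhere else, and no analysis depends on it.

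**Conclusion.** Both inconsistencies are in the current text and need reconciling.

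The wash-out conflict is of moderate severity. A patient treated 3 to 12 months before entry can pass the eligibility check while breaching Section 5.6.2. The possible carry-over bears mainly on BAFF and B-cell measures up to about the 6-month visit and on early chronic GvHD. An early influence could persist in cumulative incidence at later times, but nothing in the documents shows it. The timing rests on counting back from the first dose and taking 3 months as 90 days; the number of affected patients is unknown.

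The first-dose window is minor. It leaves the deviation status of 20 days undefined and has no bearing on carry-over.

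Three stronger readings are not supported: that the wash-out rule and the dosing window contradict each other, that the B-cell or chronic GvHD results are shown to be contaminated, and that the primary safety endpoint or the sample-size statements are affected.

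**What to change.** 1. Reconcile item 5 of the exclusion criteria (synopsis and Section 3.2) with Section 5.6.2 so that one wash-out interval applies, with a stated date from which it is counted back. The value is for clinical experts to decide.
2. Record the date of the last anti-B-cell antibody for each patient.
3. Apply the same wash-out rule when selecting bank controls.
4. Flag any patient exposed within the longer interval in the descriptive B-cell, BAFF and chronic GvHD summaries.
5. Reconcile the two statements in Section 5.2 with each other and with the synopsis, schema, Section 5 and Section 10.1, so that one first-dose window is stated.

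The cost is an amendment to the wording, one date on a case report form, and a check of the controls' medication records. Sample size and planned intervals do not change. If enrolment has already finished, steps 2 to 4 can still be done from the medical records, to the extent that these hold the dates.
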